The major difficulty in evaluating BA is preventing the control group from cross-contamination (7). In the implementation process of BA, according to the BASRCT manual, all physicians, all inpatient and outpatient staff as well as managers need to be informed and undergo basic education regarding the intervention (4). As BA addresses a prevalent and frustrating issue in psychiatric health care, there is considerable risk that the approach leaks to the control group, reducing the possibility to detect between-group differences. For example, staff have shared experiences of a change in the workplace alongside their work with BASRCT, related to a development of more positive attitudes towards all patients at the inpatient unit (11). Indeed, in BASRCT both the BA and control group demonstrated a significant within-group decrease in general psychiatric admissions.

In this project we aim to address these methodological difficulties in exploring the effects of BA, by making use of the richness of existing data in the Swedish regional and national registers (7). We will evaluate effects of implementing BA within sites, comparing data from before and after implementation. We will also compare equivalent sites which have implemented BA at different timepoints, using relevant clinical data from registers.

PROJECT DESCRIPTION

METHODS

Research questions will be evaluated through registers, i.e. no new data will be collected from individual participants. A cohort will be created including all individuals fulfilling inclusion criteria. There are two cities where the standardized version of BA is fully implemented, with a separate ward for BA (Lund and Helsingborg). Two equivalent cities of similar size and distribution, implementing the same standardized version at a later timepoint, were found (Linköping and Norrköping). In Lund, BA was implemented in 2015, as compared to 2021 in Linköping. In Helsingborg, BA was implemented in 2017, compared to 2021 in Norrköping. Retrospective data from 2010-2022 as well as prospective data, from the date of inclusion until 2025-12-31, death or moving out of the uptake area, will be used.

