National Patient Register

- Data on compulsory care (admissions and compulsory acts), Diagnoses, Age, Gender
- Motivation: primary and secondary outcome measures

National Cause of Death Register

- Cause of death
- Motivation: secondary outcome measure

The Total Population Register

- Gender, Marital status, Country of birth, Spouse or registered partner, Cohabitation, Date of death.
- Motivation: To secure that included individuals live in the uptake areas and to adjust for potential confounding factors/effect modifiers.

National Prescribed Drug Register

- Drugs retrieved from the pharmacy: Number of packages, Anatomical Therapeutic Chemical code (ATC-code), date of expiry, corresponding daily dose
- Motivation: Certain medical conditions are well captured by prescribed drugs. This is informative with regard to confounding factors/effect modifiers.

Longitudinal Integrated Database for Health Insurance and Labour Market Studies

- Income, means of subsistence, number of persons in the household
- Motivation: Obtaining information on confounding factors/ effect modifiers that we need to adjust for alternatively make separate subgroup analyses.

STATISTICAL ANALYSES PLAN

The following comparisons will be performed:

BRIEF ADMISSION BY SELF-REFERRAL FOR INDIVIDUALS WITH SELF-HARM.

Effects on compulsory care.

- Within sites, before and after introduction of BA.
- Pairwise, between equivalent sites, before BA was introduced.
- Pairwise, between equivalent sites, after BA was introduced at one of them.
- Pairwise, between equivalent sites, after BA was introduced at both.
- Between men and women, adjusted for age and diagnoses.

Overall, the studies will have good statistical power, which can be illustrated with the following example. If we assume that about 50% of the individuals receiving treatment as usual had at least one admission that was >7 days, and with 80% statistical power we want to find a significant decrease (i.e. $p<0.05$) to 25% when BA was introduced, then 66 individuals have to be included in each group. In Lund about 40 patients are recruited each year, which means that we will have at least 200 patients in each group in a five-year period. Preliminary data indicates that halving the number of days with compulsory admission is a reasonable assumption, and in addition it is also of clinical significance.

SIGNIFICANCE

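### The plan claims the early/late design can correct for other trends, but names no primary comparison and no estimator that would make the correction

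*Combined protocol and SAP*

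**What the plan says.** The final paragraph of the Area overview introduces the design: "We will evaluate effects of implementing BA within sites, comparing data from before and after implementation". It adds that equivalent sites with different start dates will also be compared, and gives neither approach precedence. Under Methods, the control sites are described this way: "Two equivalent cities of similar size and distribution, implementing the same standardized version at a later timepoint, were found". The first pair is dated: "In Lund, BA was implemented in 2015, as compared to 2021 in Linköping". The second pair is Helsingborg (2017) and Norrköping (2021).

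The statistical analyses plan lists four comparisons that bear on BA:

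- The first has no concurrent control: "Within sites, before and after introduction of BA".
- The second sets the baseline levels of a pair against each other: "Pairwise, between equivalent sites, before BA was introduced".
- The third looks at levels while a single member of the pair offers the intervention: "Pairwise, between equivalent sites, after BA was introduced at one of them".
- The fourth looks at levels once the late site has adopted it too: "Pairwise, between equivalent sites, after BA was introduced at both".

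A fifth compares men with women. The plan gives no model, no site-by-period term and no rule for using one comparison to adjust another. A primary outcome (compulsory days per year) and a primary research question are named, but the comparison that answers the question is not.

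The power example ends: "then 66 individuals have to be included in each group". It compares 50% with 25% of individuals having at least one admission longer than 7 days, and expects at least 200 patients per group at Lund over five years.

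**The concern.** The authors name the main threats themselves. Under Preliminary and previous results they accept that the roughly 50% fall in compulsory days at Lund may partly reflect outliers, fewer beds or general changes in how self-harm is managed. A before/after comparison at one site cannot separate such changes from BA. Under Methods they report that diagnostic traditions differ between sites. That is a possible source of a standing difference in level, of unknown size and direction. A comparison of levels during the period when only one site had BA would carry such a difference into the result.

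Two things are at stake. With no primary contrast, the comparison that carries the conclusion can be chosen after the results are known. And the trend correction offered as a strength of the design is not turned into an estimate that also handles a standing gap between sites.

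**Working it through.** **1. The plan's own figure.** Inputs: 50% and 25%, 80% power, p<0.05. Two-sided, without continuity correction:

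n = [1.96·√(2·0.375·0.625) + 0.842·√(0.25 + 0.1875)]² / 0.25² = 57.7

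With continuity correction: (57.7/4)·[1 + √(1 + 4/(57.7·0.25))]² = 65.4, so 66. The stated figure reproduces, for two independent groups.

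**2. What each comparison estimates.** Let the late site's level be L before and L − t after, the early site's level L − g before and L − g − t − b after. Here t is a shared fall, g a standing gap and b the BA effect.

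- Within the early site, before minus after: t + b
- Late minus early, BA at one: g + b
- Late minus early, before BA: g
- BA-at-one minus before-BA, which is the difference in change: b

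The last line is the only one that isolates b when both t and g may be non-zero. Both of its ingredients are listed in the plan; the subtraction is not.

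**3. Illustration with no BA effect.** Assumptions: the plan's binary outcome, 200 independent patients per cell, one pair, two-sided 5% tests. The sizes of trend and gap are assumed. Rates are the share of simulated runs that are significant in BA's favour.

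| Case | Within-site | BA at one | Difference in change (additive) |
|---|---|---|---|
| Both sites 50→40% | 52% | 2.4% | about 2.5% |
| Early 40→30%, late 50→40% | 56% | 56% | 2.6% (5.2% two-sided) |

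Check on the 52%: (0.10 − 1.96·√(2·0.45·0.55/200)) / √((0.25 + 0.24)/200) = (0.1000 − 0.0975)/0.0495 = 0.05, and Φ(0.05) = 0.52.

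In the second case the before-BA comparison is significant in 52% of runs, so it misses a real 10-point gap in 48%.

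**4. Scale.** Suppose both sites fall by an equal 30%, from 35% (early) and 50% (late). The additive difference in change then rejects 10.6% of the time (two-sided) and the log version about 5%. With equal 10-point falls and a 10-point gap, the log version rejects 6.4% and the additive version 5.2%.

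**5. Size and power for the difference in change.** Early site 50→25%, late site starting at 50% (assumed). With D the difference in change:

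n per cell = (1.96 + 0.842)²·Σp(1−p)/D²; power at 200 per cell = Φ(D/√(Σp(1−p)/200) − 1.96)

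With no late-site decline: Σp(1−p) = 0.25 + 0.1875 + 0.25 + 0.25 = 0.9375 and D = 0.25, so n = 118.

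| Late site ends at | D | n per cell | Power at 200 per cell |
|---|---|---|---|
| 50% | 0.25 | 118 | 95% |
| 45% | 0.20 | 184 | 83% |
| 40% | 0.15 | 324 | 60% |
| 35% | 0.10 | 719 | 32% |

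Variance relative to before/after at one site, with no late-site decline: 0.9375/0.4375 = 2.14.

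**The case against.** The strongest reply is that the plan already handles trends. The comparison with BA at only one site is concurrent, so a shared trend cancels; in the first case above it favours BA in 2.4% of runs, the nominal one-directional rate. The sites were chosen as equivalent, the inclusion criteria were broadened because diagnostic habits differ, register variables are collected for confounder adjustment, and the before-BA comparison would show a baseline gap. All of this stands, and it rules out the reading that the plan has no means of removing a trend. It is not sufficient, because equivalence rests on similar size and distribution rather than on compulsory-care levels. A reported gap is not subtracted, and a non-significant one is not shown to be zero.

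A reader might also infer that the plan, followed as written, has a particular false-positive rate. The documents do not support that. They state no rule for combining tests, and give neither size nor direction for any gap. A gap in the other direction would work against BA. The rates above belong to single comparisons under assumed conditions.

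Nor does the difference in change remove every bias. It needs parallel trends on the chosen scale, and step 4 shows that these can hold on one scale and fail on the other.

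**Conclusion.** The point holds as an omission of the primary contrast and its estimator. The control sites and the needed comparisons are already there. This should be fixed before analysis.

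Confidence in the reading of the text is high. The sizes are illustrative: they rest on the binary power example, independent cells and assumed trends and gaps. They do not concern days per year, for which the documents give no standard deviation.

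It would go too far to say that the study is underpowered. With 200 per cell and no late-site decline, one pair has 95% power for the difference in change, and two pairs are planned. What the documents do not support is carrying the statement of good power over to the trend-corrected question, where power depends heavily on how far the late sites decline on their own.

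**What to change.** Name one primary contrast: the early-minus-late difference in change in days with compulsory admission per year, that is, the BA-at-one comparison minus the before-BA comparison. Pool it over the two pairs, with site and calendar-year effects, over matched calendar periods that end before the late sites adopt BA in 2021.

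Fix the scale in advance. One option is a rate ratio from a log-link count model, with the additive difference as a sensitivity analysis. Use intervals that allow for repeated measures on the same people, show site-by-year variation as a sensitivity analysis, and report the pre-BA trends in each pair. Label the listed comparisons, including those using data after 2021, as supportive.

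State that 66 per group applies to a two-group comparison, and give power for the primary contrast over a range of late-site declines.

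The cost is SAP wording and some analysis work on data already planned. The drawbacks are about 2.1 times the variance of a before/after comparison in a single pair, a less favourable power statement if the late sites also decline, and reliance on parallel trends with only four sites. A local change at one site, such as a bed reduction, would still not be removed.

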The proposed study will fill important knowledge gaps addressing potential implications of BA for compulsory care, which appears to have decreased substantially at clinics where BA has been implemented, according to preliminary data. A longitudinal register-based study, following a cohort in sites where BA is fully implemented and comparing it to a cohort in equivalent sites where BA is implemented at a later timepoint, will avoid potential contamination of educating all staff on the intervention. It will also enable correction for effects of other trends in health care during the last decade, e.g. those introduced by national initiatives such as the Swedish National Self-Injury Project (14) and *Bättre vård, mindre tvång* (“Better care, less coercion”; 15). Such a study will add to previous research and will, to the best of our knowledge, be the first of its kind.

PRELIMINARY AND PREVIOUS RESULTS

Our research group evaluated BA in a randomized clinical trial among persons with self-harm and traits of BPD in four adult psychiatric clinics in Skåne (7). We found that both the group with access to BA and the control group showed significant decreases in days admitted to the hospital and in visits to the emergency department, but only the BA group showed a significant decrease in duration of compulsory admissions and frequency of NSSI. No significant between-group differences were found in these variables. We also found an increase in several dimensions of daily life functioning in the BA group, that were not found in the control group. Furthermore, we have explored the lived experiences of individuals with life-threatening self-harm behavior and previous extensive experience of hospital admissions (compulsory and voluntary), as well as the experiences of the staff caring for them (10, 11).

BRIEF ADMISSION BY SELF-REFERRAL FOR INDIVIDUALS WITH SELF-HARM.

Effects on compulsory care.

For these individuals, BA was described as a safe and worthy respite, without triggers aggravating self-harm, which may lead to compulsory admissions.

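### The within-site before/after comparisons have no trend control, and from 2021 no unexposed site remains, so later changes can be trend-corrected only under a stable-effect assumption that the plan does not state

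*Combined protocol and SAP*

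**What the plan says.** The Methods section gives the start years: "In Lund, BA was implemented in 2015, as compared to 2021 in Linköping" and "In Helsingborg, BA was implemented in 2017, compared to 2021 in Norrköping". No months are given. The data window is "Retrospective data from 2010-2022 as well as prospective data, from the date of inclusion until 2025-12-31".

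The Statistical Analyses Plan lists the comparison "Within sites, before and after introduction of BA", with no restriction by site and no end to the after-BA period. The last paragraph of the Area Overview presents this comparison as a way to evaluate the effects of implementing BA. Three between-site comparisons follow in the list: "Pairwise, between equivalent sites, before BA was introduced", "Pairwise, between equivalent sites, after BA was introduced at one of them" and "Pairwise, between equivalent sites, after BA was introduced at both". The plan does not say how the within-site and pairwise lines are combined, specifies no model or calendar-time term, and names no comparison as primary.

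On trends, the Significance section says of the early/late design: "It will also enable correction for effects of other trends in health care during the last decade". The section on preliminary results concedes that the fall seen at Lund may have other explanations, including fewer beds and general changes in how self-harm is managed.

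**The concern.** A before/after change at one site is the BA effect plus whatever else changed over the same years. Separating the two needs a comparator that went through those years without the same change in exposure. In this design an unexposed paired site exists at Lund for 2015 to 2020 and at Helsingborg for 2017 to 2020. It does not exist at any site once BA starts in Linköping and Norrköping.

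The trend-correction claim in the Significance section carries no such limit. If the within-site line is reported for all four sites, four falls could be read as four confirmations of a BA effect. Only the two early sites have an unexposed control, and only for part of their after-BA period. The two late-site falls could be produced entirely by a national change. The plan's own preliminary section takes that kind of explanation seriously for Lund.

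**Working it through.** **Inputs.** From Methods: BA starts in 2015 (Lund), 2017 (Helsingborg) and 2021 (Linköping and Norrköping); data run from 2010 to the end of 2025. From the Statistical Analyses Plan: 50% versus 25%, 80% power, p<0.05, 66 per group, about 40 patients a year at Lund, at least 200 per group. The yearly trend is an assumption, because the documents give none.

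**The plan's own figure.** Two proportions, 50% versus 25%, two-sided 5%, 80% power, with continuity correction, gives 66 per group, as stated. The point here does not depend on it.

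**Step 1: years without an unexposed partner.** Start years and 2021 are counted as exposed.
- Lund: 2015–2025 is 11 after-BA years; 2021–2025 is 5; 5/11 = 45%.
- Helsingborg: 2017–2025 is 9 years; 5/9 = 56%.
- Both early sites: 10/20 = 50%.
- Linköping and Norrköping: 5 of 5 each.

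The early-site share depends on convention. Pooled, it is 10/18 = 56% if the early sites' start years are dropped, 8/20 = 40% if 2021 counts as unexposed, 4/14 = 29% if data stop in 2022, and 2/14 = 14% if both of the last two apply. The late-site share is 100% throughout.

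**Step 2: apparent effect with no BA effect.** Assume the same yearly decline r at every site, so the rate in year y is proportional to (1−r)^(y−2010). Apparent fall = 1 − (mean over after-BA years) / (mean over before-BA years). For the late sites at r = 2%: 1 − 0.7693/0.9058 = 15.1%.

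| Within-site comparison | 2%/yr | 3%/yr | 5%/yr | 8%/yr |
|---|---|---|---|---|
| Late sites, 2010–20 vs 2021–25 | 15.1% | 21.9% | 34.4% | 50.1% |
| Lund, 2010–14 vs 2015–25 | 14.8% | 21.3% | 33.0% | 47.2% |
| Helsingborg, 2010–16 vs 2017–25 | 14.9% | 21.5% | 33.4% | 48.2% |
| Lund cut at 2020, 2010–14 vs 2015–20 | 10.5% | 15.4% | 24.5% | 36.6% |

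The bias is nearly equal at all four sites, so it comes from the missing control. Cutting Lund at 2020 reduces it but does not remove it.

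**Step 3: the part specific to 2021 onward.** Assume instead a one-off national drop of 20% from 2021. It shows as 20% at the late sites, 20% × 5/11 = 9.1% at Lund and 20% × 5/9 = 11.1% at Helsingborg.

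**Step 4: what a difference in change does.**
- *Up to 2020.* Divide Lund's after/before ratio (2015–20 over 2010–14) by Linköping's over the same years. Under a common proportional trend and no BA effect, both ratios are equal and the result is 1.00.
- *From 2021.* Divide the late site's ratio by that of its already exposed partner. With a common fall of 20% and a stable early-site effect: 0.80/0.80 = 1.00. If the early-site effect deepens by a further 10% or 20% (assumed): 0.80/(0.80 × 0.90) = 1.11 or 0.80/(0.80 × 0.80) = 1.25, a bias against BA.

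**Step 5: chance of a false finding.** Use the plan's example outcome (50% with an admission over 7 days), assume 200 per group at a late site and no BA effect. A common fall of 10%, 20% or 30% then gives a significant decrease with probability of about 17%, 52% or 86%.

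**The case against.** The strongest reply is that the pairwise comparisons already supply the pieces of a difference-in-change analysis, and that they split where the second site starts BA. This stands. A reader might infer that the whole plan reads any national change as BA, or that nothing can correct the late-site results. The documents support neither. Before 2021 the unexposed partner removes a common trend. After 2021 the already exposed partner can still do so if its own BA effect is stable. What is missing is the rule that combines the comparisons and the statement of that assumption.

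It is also fair to say that the table above does not isolate a problem of the years from 2021, since the early sites show nearly the same falls. That stands too, and it is why shortening the early-site window is not enough without a control.

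A reader might further infer that the plan pools early- and late-site estimates, gives the late sites confirmatory status or claims replication at four sites. It says none of these. The risk lies in how an unqualified within-site line could be reported. The Area Overview does attach the language of effects to that line, so the labelling point remains.

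**Conclusion.** The point holds in this form. The within-site comparisons are uncontrolled at all four sites. Control by an unexposed partner is available only at Lund (about 6 years) and Helsingborg (about 4 years). All after-BA years at the late sites, and roughly half of those at the early sites under the main counting convention, depend on an unstated stable-effect assumption.

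The size of the error depends on a trend that the documents do not give. Over 2 to 8% per year, the false fall at the late sites runs from 15 to 50%. Its upper end matches the halving of compulsory days that the plan calls a reasonable assumption. The calculation assumes the same proportional trend everywhere and whole-year exposure. The unexposed-partner contrast also rests on parallel trends within each pair, which the comparison of paired sites before BA can help to check. This should be settled before analysis; it does not undermine the design.

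**What to change.** In the Statistical Analyses Plan:
1. Base the BA-effect claim on the difference in change between each early site and its paired late site, using data up to the day before BA starts at the late site. State the start dates.
2. Label all within-site before/after comparisons as descriptive, and do not count late-site falls as independent replication.
3. If a late-site effect is wanted, subtract the early partner's change over the same years, with the before-period starting only once the partner has BA. Report it as secondary, state the stable-effect assumption, and note that a still-deepening early-site effect biases the result against BA.

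In the Significance section:

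4. Say that trend correction against an unexposed site applies only before the 2021 introductions.

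The cost is wording and one analysis cut on data already planned. The downside is fewer after-BA years in the main contrast: about 6 instead of 11 at Lund and 4 instead of 9 at Helsingborg. At about 40 patients a year Lund would have about 6 × 40 = 240. No rate is given for Helsingborg; at Lund's rate (assumption) it would have about 4 × 40 = 160, below the stated 200 but above 66. The figure of 66 is for a simple two-group comparison of proportions, so it is only a rough guide to the precision of a difference in change.

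### The plan relies on the later-implementing sites to correct for background trends, but specifies no trend comparison and no contrast that makes the correction

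*Combined protocol and SAP*

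**What the plan says.** The protocol and SAP are one document. Under Methods, the comparison sites are introduced as "Two equivalent cities of similar size and distribution" that took up the same standardised BA later. For the first pair the dates are: "In Lund, BA was implemented in 2015, as compared to 2021 in Linköping". For the second pair they are 2017 (Helsingborg) and 2021 (Norrköping). Retrospective data start in 2010 and follow-up runs to the end of 2025. The primary outcome is days with compulsory admission, expressed per year.

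The Statistical Analyses Plan lists five comparisons. One sets each site's results after BA started against its own earlier results. Three set the paired sites against each other: "Pairwise, between equivalent sites, before BA was introduced"; then while only the early site has BA; then once both have it. The fifth contrasts men with women, with adjustment for age and diagnoses.

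No model, time term, site-by-period contrast or criterion accompanies the list. The Significance section nevertheless claims for the design: "It will also enable correction for effects of other trends in health care during the last decade". The section on preliminary results accepts that the roughly 50% fall at Lund may have other explanations, including outliers, fewer beds and general changes in how self-harm is managed.

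**The concern.** A late site can stand in for the early site's background trend only if, without BA, the two would have moved in parallel on the scale of the analysis. Similar city size does not establish this, and neither does a similar average of compulsory care before BA. Two sites can share an average while moving apart, and two sites with different averages can move in parallel.

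The plan does not commit to looking at pre-BA trends, and it does not combine the before/after and between-site comparisons into one estimate. If compulsory care was already falling faster at the early site, its lower rate after BA could be that earlier divergence continuing, and the listed comparisons, taken one by one, need not reveal it. At stake is whether a difference on the primary outcome can be attributed to BA.

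**Working it through.** **The plan's own figure.** The only calculated figure in the SAP is 66 per group for 50% versus 25% with 80% power at p<0.05. The usual two-proportion formula gives [1.96·√(2·0.375·0.625) + 0.842·√(0.25 + 0.1875)]² / 0.25² = 57.7, so 58. With the continuity correction, (57.7/4)·[1 + √(1 + 4/(57.7·0.25))]² = 65.4, so 66. It reproduces (two-sided, continuity-corrected) but has no bearing on site trends.

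**Inputs for the trend check.** BA dates and the 2010 data start come from Methods. The implementation year is counted as post-BA, and the post-BA window ends in 2020, the year before the late sites start. Pre-BA slopes are not in the documents, so the values below are assumptions.

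1. Distance between window midpoints.
   - Lund/Linköping: pre 2010–2014 (5 years, midpoint 2012), post 2015–2020 (midpoint 2017.5). Distance 5.5 years.
   - Helsingborg/Norrköping: pre 2010–2016 (7 years, midpoint 2013), post 2017–2020 (midpoint 2018.5). Distance 5.5 years.

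2. Equal level is not sufficient. Suppose the average log rates are equal before BA, the log-scale slopes differ by a constant d per year, and BA has no effect. The later early/late ratio is then exp(−5.5·d):
   - d = 0.03: exp(−0.165) = 0.85
   - d = 0.05: exp(−0.275) = 0.76
   - d = 0.08: exp(−0.440) = 0.64
   - To mimic the halving that the SAP calls reasonable: d = ln 2 / 5.5 = 0.126, a relative decline of 1 − exp(−0.126) = 11.8% per year.

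   A check with compounded declines and arithmetic means over each window gives, at 2%, 5% and 10% per year, 0.90, 0.76 and 0.56 (Lund pair) and 0.89, 0.75 and 0.55 (Helsingborg pair). If the implementation year is dropped, the distance becomes 6.0 years and the halving needs 10.9% per year.

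3. A difference-in-differences alone does not remove this. With a pre-BA ratio of 1.00, the ratio of ratios at d = 0.05 is 0.76/1.00 = 0.76. The pre-BA slope has to be examined as well.

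4. Equal level is not necessary. If the early site is 1.30 times the late site both before and after, the ratio of ratios is 1.30/1.30 = 1.00 and nothing spurious arises on the log scale.

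5. Yearly data would show what an average hides. At d = 0.05 in the Lund pair, the early/late ratio moves from exp(0.10) = 1.11 in 2010 to exp(−0.10) = 0.90 in 2014, around a mean of 1.00.

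6. How well the slope can be estimated. Let s be the yearly scatter of the log ratio (not given in the documents).
   - Five annual points: the 95% half-width of the slope is 3.182·s/√10 ≈ 1.0·s. Carried over 5.5 years it is about 5.5·s, which exceeds ln 2 = 0.693 once s passes about 0.125.
   - Seven points: 2.571·s/√28 ≈ 0.49·s, or about 2.7·s over 5.5 years, with a threshold near 0.26.

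**The case against.** A reader might infer that the plan tests levels only, pools the pre-BA years into one number, and declares sites equivalent when the test is not significant. The documents do not support this. The pre-BA comparison is listed without an estimand. The outcome is in days per year and the study is described as longitudinal, so a year-by-year comparison fits the text equally well. The equivalence label is assigned in advance from city characteristics; it is not the result of a test, and no pass rule exists.

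Other planned comparisons also bear on the threat. If a lower rate at the early site were only an old trend, the gap should keep widening after 2021 with no shift at the late sites, whereas a similar BA effect at both would tend to narrow it. Two pairs with different early starts add some replication. This stands in part: the pre-BA comparison is not the only safeguard. But the plan does not say how these results would be combined or read, and a trend shared by both early sites would push both pairs the same way.

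The slopes are hypothetical, and mimicking the full halving needs about 12% per year sustained across 2010–2020. That also stands. Finally, requiring the effect to survive extrapolation of the slope limits would be too severe: by step 6, with an observed slope difference of zero, even an exactly estimated halving in the Lund pair would fail once s exceeds about 0.125.

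**Conclusion.** The concern holds as a gap between claim and method. The document claims a correction for trends, but the plan contains neither an assessment of parallel trends nor a contrast that performs the correction, and it leaves open whether the pre-BA comparison concerns level or trend. The label of equivalence does not fill the gap, because it rests on size and distribution.

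Under assumed divergences of 3% to 8% per year, constant on the log scale with equal pre-BA averages, the spurious early/late ratio would be about 0.85 to 0.64, a material share of the halving the plan anticipates. These figures show sensitivity only. The documents give no pre-BA trend for any site, so they do not support a conclusion that the pairs were diverging or that an observed BA effect would be spurious. The point should be settled in the SAP before analysis, and the data already planned allow it.

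**What to change.** Add to the Statistical Analyses Plan, for each pair:

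1. A figure of the early-minus-late difference in compulsory days per year by calendar year, or in finer units, from 2010. State the scale of analysis (absolute difference or log ratio), since parallel trends on one scale need not hold on the other.
2. The pre-BA slope difference with its 95% interval, and a statement that a non-significant difference will not be read as proof of equal trends.
3. The BA effect as a difference-in-differences contrast: the change at the early site minus the change at the late site over the same calendar years, up to the late site's start.
4. A sensitivity estimate that allows the pre-BA slope difference to continue, reported alongside the main estimate and not as a pass/fail gate, because five or seven annual points make the extrapolated interval very wide.

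It would also help to say how the comparison after both sites have BA, and the before/after comparison at the late sites, will be read together with this contrast.

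The cost is SAP text, one figure per pair, a little more analysis, and a sensitivity interval that will be wider and less favourable. No new data are required.
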